Title: Effects of using the Duracore Splinting Device on Patient Outcomes Related to Chest Trauma

Protocol Version Number: 3

Protocol Version Date: 12/8/2020

CHIRB IRBNet ID: 1517921-3

1) Investigators

Principal Investigator

[name] Title: Registered Respiratory Therapist Department: Respiratory Therapy [contact] Email: [contact]

Co-Investigator:

[name] Title: Registered Respiratory Therapist Department: Respiratory Therapy [contact] Email: [contact]

Co-Investigator:

[name] Title: Registered Respiratory Therapist Department: Respiratory Therapy [contact] Email: [contact]

Co-Investigator:

[name] II, M.D. Title: Surgical Trauma Physician Department: Trauma Services Email: [contact]

2) Funding Source

Financial funding was obtained by grants from local agencies through application processes, along with interviews and assessment of the medical device. The first grant was obtained through the Southern Colorado Society of Respiratory Care in hopes to obtain better choices for treatment for patients with rib fractures. Additional funding was provided by the Penrose Foundation as well.

3) Objectives and Hypothesis(es)

The purpose of this study is to use the Duracore patient operated torso splinting device for patients with chest trauma, including rib fractures, to improve deep breathing and help with reduced hospital length of stays (LOS). The hypothesis of this study is that the use of the Duracore splinting device will reduce hospital length of stays and improve patient lung capacities over the course of admission following chest trauma.

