The study will use a randomized-experimental design and will be randomized via envelope randomization, with experimenters being blinded. A total of 104 patients, 26 in each group, will undergo initial incentive spirometry and force vital capacity (FVC) and FEV₁ tests. Groups will consist of a control versus experimental group, stratified into bilateral and unilateral rib fractures. Three days' worth of data will be collected for each of the tests and will also be collected 24 hours prior to discharge. Length of stays will be compared for experimental and control groups, as well as time to ambulation (collected from the first physical therapy assessment). Injury severity score will also be collected to determine any correlation by severity of injury. Patient satisfaction surveys for the device will also be collected to determine if the patients feel a difference with the device.

4) Background/Scientific Rationale and Significance

Little research as been conducted to determine the significance of a splinting device used in patients with chest trauma, and it is still uncertain whether these devices improve overall patient outcomes. Contradicting studies with similar experimental designs show either some significance (p-value) or insignificance in pulmonary function pre- and post-treatment. This gap in current knowledge leaves room for concern in whether the patient truly benefits from a splinting device in this type of injury. Changes in percent predicted FVC/FEV₁ ratio in this patient population are not readily demonstrated in most of these studies, as well as differing length of stays. This study will contribute to this base of knowledge by determining the effects of the Duracore splinting device on this patient population using the objectives.

5) Inclusion and Exclusion Criteria

Inclusion:

- Adult patient admitted to the trauma service at Penrose Hospital
- Willing and able to comply with all requirements of the study
- Active diagnosis of rib fractures
- Male or female ages 18 and older
- Able to provide written informed consent to participate in the study
- Must be physically able to don and use the splinting device independently without assistance

Exclusion:

- <18 years old
- History of pulmonary disease, lobectomy, or lung transplant
- Current smoker of tobacco products >5 years
- Diagnosis of flail chest

- Pregnant Women
- Prisoners
- Cognitively Impaired; must be alert and oriented x 3

6) Number of Subjects

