Number of subjects was based on a power analysis using FVC/FEV₁ as the primary variable and stratified by unilateral versus bilateral diagnosis. Previous literature suggests a standard deviation of approximately 0.20-0.60 for FVC/FEV₁ values. SD was set at 0.40. Unilateral control was estimated to be 50% of predicted values (FVC/FEV₁) due to the nature of the injury, set at approximately 1.50L, with bilateral set at approximately 1.35L. Unilateral experimental group means were increased by 20% of predicted values to 1.80L, and bilateral to 1.50L. The required sample size to achieve 80% power to detect difference between splint and control groups is 104, with each group requiring 26 subjects each. Power calculations were performed in R version 4.0.0 with the pwr2ppl package, using the anova2x2 function.

Number of subjects to be used are 150 to account for withdrawals, incomplete data sets, extraneous results, etc. This is a single site study.

7) Recruitment Methods

Respiratory Therapy is part of the trauma multi-disciplinary team. and is involved with the care of every trauma patient admitted to Penrose Hospital. During trauma rounds in the ICU and floor patients that met criteria for the study will be identified. The investigators will approach those identified patients for potential enrollment in the study. Note they will not approach any patient for consent that is under their care that shift. There are no flyers or advertisements for this research or device.

8) Study Timelines

It is estimated that it will take at least one year to complete this study to include enrollment, subject completion, and all analysis. All primary variables and analyses should be completed by this time.

9) Study Endpoints

The primary endpoint of this study is to investigate the use of the Duracore splinting device in patients with chest trauma. Hospital length of stays, time to ambulation, a patient satisfaction survey, incentive spirometry, forced vital capacity measurements, and the injury severity score will be correlated to a control group to determine its' effectiveness. The quantitative data points will be collected over the first three days of hospital stay and 24 hours prior to discharge. The qualitative data will be collected prior to patient discharge. The hypothesis of this study is that the use of the Duracore splinting device will reduce hospital length of stays and improve patient lung capacities over the course of admission following chest trauma.

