Variables to be collected are:

- Age (years)
- Gender
- Diagnosis

CHI Institute for Research and Innovation

- Incentive Spirometry values for this admission
- FVC/FEV1 values for this admission
- Height, Weight, and Ethnicity for FVC/FEV₁ % predicted calculation
- Averages from the patient satisfaction survey using a Likert Scale
- Length of Stays
- Time to Ambulation
- Injury Severity Score

10) Procedures Involved

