The design of this study is a randomized experimental trial. The procedures involved in this study will first include obtaining the individual's consent to participate. Incentive spirometry is a standard of care that has been proven to improve deep breathing for patients. FVC/FEV₁ measurements are not always routinely done at this site but has been proven to be an indicator in respiratory deterioration in this population. Enrollment of each subject will be on a one to one basis for control and experimental groups. The trial will be randomized to reduce bias by randomly selecting patients between control and experimental groups by alternating every other patient receiving the treatment. Height, sex, ethnicity, and age will be accounted for as well to calculate the percent predicted FVC/FEV_1 to reduce statistical error. Enrollment will be based on patient consent. After enrollment into the study after admission to the hospital, baseline values of incentive spirometry (IS) and spirometry will be done. The patient will then be placed in the experimental or control group after being assigned a group via envelope randomization. If the patient is under experimental, they will receive a splinting device for treatment. Control groups will receive standard of care treatment without the splinting device. Continued analysis of IS and FVC/FEV₁ will occur over three days, and a final collection prior to discharge. Discharge planning will be coordinated with respiratory therapy, so the patient does not go home without completing the survey and final analysis. The patient satisfaction survey will be a paper survey administered to the patient. Patient identifying information will not be present on this form to maintain confidentiality. The patient will be asked if they would like to complete the form and that it is an anonymous short survey to help with identifying how the patient felt about the research. The subject will only be enrolled in the study for the duration of their hospital stay as an inpatient. There will be no follow-up after discharge, and any patients who are discharged without completing the final analysis will be omitted from the study.

11) Data Analysis Plan

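### Discharge is planned around the study's final test and survey, and patients who miss the test are dropped, so study logistics can enter length of stay, a hypothesised outcome with no stated stop time

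*Combined protocol and SAP*

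**What the plan says.** Section 3 (Objectives and Hypotheses) states that "the use of the Duracore splinting device will reduce hospital length of stays and improve patient lung capacities over the course of admission", and its design paragraph adds: "Length of stays will be compared for experimental and control groups". Section 9 (Study Endpoints) puts length of stay first among the measures of effectiveness. The variable list in that section gives it only by name, "Length of Stays", with no start time, stop time or readiness criterion.

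On the timing of measurements, Section 9 says: "The quantitative data points will be collected over the first three days of hospital stay and 24 hours prior to discharge". Section 10 (Procedures Involved) then says: "Discharge planning will be coordinated with respiratory therapy, so the patient does not go home without completing the survey and final analysis". The same section presents the survey as something the patient may choose to fill in. It closes with the rule that "any patients who are discharged without completing the final analysis will be omitted from the study". Section 13 (Withdrawal of Subjects) treats the same patients differently: they may be withdrawn, and their data are kept unless the subject specifies otherwise.

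On who is involved, Section 18 says that the respiratory therapy department is not directly involved in the research, but counts the investigators among the therapists who perform the procedures. Sections 3 and 11 describe experimenter blinding. No section says whether those who plan discharge know the arm.

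**The concern.** The time at which a patient leaves is both an outcome and something that a study procedure is arranged around. If departure waits on the last spirometry session or the survey, that wait is recorded as hospital stay, and the outcome mixes recovery with study scheduling. The final measurement is set 24 hours before discharge, so someone must anticipate the discharge, and a late test is a plausible source of waiting.

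Two routes to error follow.

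- **Waiting.** A wait that differs between arms shifts the estimated effect on stay in either direction.
- **Omission.** Dropping patients who leave without the final test selects on the circumstances of discharge, which are closely tied to the outcome being compared.

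At stake is whether a reader can interpret a difference in stay, or the absence of one, as an effect of the device.

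**Working it through.** **1. The plan's own figure.** The only sample-size calculation concerns FVC/FEV1 (Sections 6 and 11). The splint effect averaged over strata is (0.30 + 0.15)/2 = 0.225, with SD 0.40 and 26 per cell. Alpha is not stated; 0.05 two-sided is assumed. The noncentrality is 26 × 0.225² / 0.40² = 8.23 on 1 and 100 degrees of freedom. This gives power 0.811, and 25 per cell gives 0.795. The 104 therefore reproduces. It supplies the 52 per arm used below, but says nothing about length of stay.

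**2. How a wait enters the comparison.** Let a share p of an arm be delayed by d days. The arm's mean stay rises by p × d, and the arm difference shifts by (p_E − p_C) × d, where E is the splint arm and C is control.

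- Equal shares, 20% in each arm, d from 0.125 to 1.0 day: each arm rises by 0.025 to 0.20 day and the difference shifts by 0.
- Unequal shares, 30% against 10%, same d: the difference shifts by 0.025 to 0.20 day, in either direction.

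The added noise is small. With SD 2 days and half of the patients delayed by a full day, the SD becomes √(4 + 0.5 × 0.5 × 1²) = 2.06.

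**3. Effect on the false-positive rate.** The documents give no length-of-stay SD, target difference or expected delay, so SDs of 2 and 3 days are assumptions. With no true effect and a spurious mean difference δ, the standard error is SD × √(2/52), which is 0.392 for SD 2 and 0.588 for SD 3. The rejection probability comes from the noncentral t with noncentrality δ/SE and 102 degrees of freedom, two-sided at 0.05.

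| Spurious mean difference | SD 2 days | SD 3 days |
|---|---|---|
| 1 hour (0.042 day) | 5.1% | 5.1% |
| 2 hours (0.083 day) | 5.5% | 5.2% |
| 0.20 day | 8.0% | 6.3% |
| 6 hours (0.25 day) | 9.7% | 7.1% |
| 12 hours (0.50 day) | 24.3% | 13.4% |

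These are differences between whole-arm means, not waits in single patients. A 12-hour mean difference would need, for example, half of one arm to wait a full extra day and nobody in the other. With an assumed SD of 5 days, 6 hours gives 5.7% and 12 hours gives 8.0%.

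**4. The passages side by side.** Section 10 first says that patients do not go home before the survey and final test, then says what happens to those who do. It makes the survey a choice, yet names it as something completed before going home. Section 10 omits patients who miss the final test; Section 13 says that they may be withdrawn and keeps their data. The plan does not settle whether these patients count in the length-of-stay comparison.

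**The case against.** The strongest reply is that Section 10 speaks of coordinating discharge planning, which is scheduling language. The final test is meant to happen during the stay, and the omission rule shows that patients can leave without it. A stated aim followed by a contingency is ordinary drafting. This largely stands. A reader might infer that patients fit to leave are held back for study tasks, but no section says so. What remains is that the stated purpose of the coordination is to complete study tasks before departure, and no section says that any resulting wait is excluded from length of stay.

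A reader might also infer that unblinded study staff control discharge. The documents do not support that as fact. The text names respiratory therapy, Section 18 says that the department is not directly involved, and Sections 3 and 11 claim experimenter blinding. The supportable statement is narrower: the device is visible, investigators are among the therapists performing procedures, and blinding of discharge planners is not described.

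On size, the tasks are a spirometry session and a short survey, so a mean difference of 6 to 12 hours lies at the extreme. That is accepted. Section 11 also names the t-test for incentive spirometry and FVC/FEV1, and only correlations for length of stay. The t-test in the table therefore illustrates the between-arm comparison announced in Section 3; it is not the plan's specified analysis.

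Finally, if planning is coordinated with study tasks, the discharge order may itself be timed around them, so order time is not a full remedy. That also stands.

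**Conclusion.** The point holds as a weakness in the definition and handling of length of stay. It is not evidence that the comparison will be biased. The plan leaves room for study logistics to enter a hypothesised outcome, and for patients to be removed because of how they were discharged.

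An equal wait costs a little precision and shifts the difference by zero. An unequal wait biases it, and nothing in the documents rules one out. Under the assumed SDs of 2 to 3 days, 52 per arm and two-sided 0.05, the inflation is negligible for a mean difference of 1 to 2 hours (5.1% to 5.5%) and modest at 0.2 day (6.3% to 8.0%). It is serious only at 12 hours (13.4% to 24.3%). The last range should not be read as the expected error rate. The selection caused by omission is a related problem that needs no waiting at all, and the documents give no figure from which to size it.

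The change is worth making because it is cheap, and because a wait not time-stamped during the trial may be hard to reconstruct afterwards.

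**What to change.** In Sections 9 and 11:

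- End length of stay at the time-stamped discharge order, or at documented readiness for discharge, and not at physical departure. State the start time too; which start is chosen is a separate matter from this point.
- Record the gap from order to departure for every patient and report it by arm. State that order time may itself be influenced by coordinated planning, so a small gap does not prove that there was no study-related wait.
- Keep all randomised patients in the length-of-stay comparison. Treat a missed final test or survey as missing data for that measure only.

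In Sections 10 and 13, reconcile the three statements on patients who leave early (they do not go home before completion, they are omitted, they may be withdrawn), and reconcile the optional survey with the expectation that it is completed before going home.

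The cost is a few sentences of outcome definition and one further time-stamp from the chart. The drawback is that order time is an imperfect marker of readiness. No change to discharge practice is proposed.

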Subjects may voluntarily withdraw from the study at any time during their admission. Subjects may be withdrawn from the study if they are discharged prior to final analysis, deterioration of health rendering them incapable of participating in research, or verbal authorization to remove them from the study. Subjects may be removed in the case that the protocol needs to be revised due to an unforeseen adverse event that would exclude them from the study. All data will be retained unless specified by the subject up to the required date.

14) Risks to Subjects

The risk to subjects is extremely minimal. Chest trauma is consistently treated with incentive spirometry and monitored with FVC/FEV_1 percent predicted values. There is very little risk to the patient with these procedures, and only some discomfort and pain from the rib fractures may be associated. The difference is the addition of the splinting device. Splinting devices are routinely used in the hospital for open heart patients and produces no associated risk to those patients. It is unlikely that this splinting device will produce any adverse events. The device is unrestrictive and only splints the chest when the patient wants it to. The only

CHI Institute for Research and Innovation

potential risks are some discomfort, and an unknown allergy to the urethane coated polyester fabric on the device.

15) Potential Benefits to Subjects

Potential benefits to the subjects are unknown currently.

16) Sharing of Results with Subjects

Specific study results will not be shared with subjects

17) Setting

Potential subjects will be recruited at Penrose Hospital in Colorado Springs, CO.

18) Resources Available

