Research staff oversee enrollment and follow-up of subjects throughout their hospital stay. They are responsible for data collection and retention, as well as education of secondary hospital staff that will be seeing the device. The respiratory therapy department will perform the procedures because they are a standard of care. The department will not be directly involved in this research activity and will only be performing normal ordered procedures with the patients. All staff performing procedures are board certified and state-licensed respiratory therapists, and it is within their scope of practice to perform these procedures. This includes investigating staff. Nursing staff will also reinforce incentive spirometry use, which is a standard of care. Investigators will be the **only** people to be collecting relevant data from the chart. All relevant staff in the hospital will be educated on what the device is by investigators to better introduce the device into the work environment. Should it be necessary, the hospital is a place of availability for any medical or psychological need during the subjects' length of stay. This is the site in which all procedures and experimental data will be collected.

Penrose Hospital is a level I verified trauma center and receives patients with rib fractures and pulmonary contusions regularly. The sample size is justified statistically and is relevant to account for withdrawals. The actual sample size only needs to be 70% of the specified 150 to provide statistical significance.

19) Prior Approvals

The Duracore chest splint was presented at the trauma-research meeting May 2, 2019. Approval was granted for trial of the device pending modification of the device to include a removable shell for trial phase. Received financial assistance through approval of application process from the Southern Colorado Society of Respiratory Care for the Duracore chest splint for trial.

20) Confidentiality

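### Patients who go home without the final test are dropped from the whole study after randomization, including from length of stay and time to ambulation, which do not need that test

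*Combined protocol and SAP*

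**What the plan says.** Section 10 (Procedures Involved) gives the sequence: consent, baseline incentive spirometry (IS) and spirometry, then allocation: "The patient will then be placed in the experimental or control group after being assigned a group via envelope randomization". IS and FVC/FEV1 are repeated over three days, with a last collection before discharge. The section then says that "any patients who are discharged without completing the final analysis will be omitted from the study". It also describes a safeguard: "Discharge planning will be coordinated with respiratory therapy, so the patient does not go home without completing the survey and final analysis". The final analysis is not formally defined. It is listed apart from the survey, so in context it means the last IS and FVC/FEV1 collection. Section 9 (Study Endpoints) gives the timing: "The quantitative data points will be collected over the first three days of hospital stay and 24 hours prior to discharge".

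Section 3 (Objectives and Hypothesis(es)) puts stay in the hypothesis, namely that "the use of the Duracore splinting device will reduce hospital length of stays", and plans the comparison: "Length of stays will be compared for experimental and control groups, as well as time to ambulation". It takes time to ambulation from the first physical therapy assessment. Section 18 (Resources Available) makes the investigators the sole "people to be collecting relevant data from the chart".

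Section 13 (Withdrawal of Subjects) treats the same event differently: "Subjects may be withdrawn from the study if they are discharged prior to final analysis". It adds that data are kept unless the subject asks otherwise.

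**The concern.** The rule acts after allocation, is mandatory, and removes the patient from the study rather than from the one analysis that lacks a value. Length of stay is known once the patient leaves, and time to ambulation is recorded by physical therapy, so a missed breathing test deletes data already observed on both. The patient's baseline and daily FVC/FEV1 values go too.

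What triggers omission is leaving hospital before a test, and the timing of leaving is itself one of the outcomes. Once anyone is omitted on this ground, stay is no longer compared between the groups as randomized. Nothing in the documents shows whether short or longer stays would miss the final test more often, so no direction of bias can be asserted.

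**Working it through.** **1. The plan's own figures.** Section 6 gives SD 0.40 and means of 1.50 v 1.80 L (unilateral) and 1.35 v 1.50 L (bilateral). The main effect of the splint is (0.30 + 0.15)/2 = 0.225 L. With a two-sided alpha of 0.05 (assumed, as the plan states none) and a noncentral F with N − 4 degrees of freedom, 26 per cell gives 81.1% power and 25 gives 79.5%. The stated 104 therefore reproduces. Enrolling 150 allows 150 − 104 = 46 losses from all causes (46/150 = 30.7%). The concern does not depend on this sample size.

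**2. Which outcomes need the final test.**

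| Outcome | Source | Needs the final test? |
|---|---|---|
| Length of stay | Known at discharge | No |
| Time to ambulation | First physical therapy assessment | No |
| Baseline and daily IS, FVC/FEV1 | Earlier tests | No |
| Pre-discharge IS, FVC/FEV1 | Final collection | Yes |

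**3. Illustration of bias in length of stay.** The documents supply none of the inputs, so all are assumptions: log-normal stay, log-SD σ = 0.7, control median 5 days, true 20% reduction (device median 4 days), and short stay meaning under 3 days. The omission rule is the same in both arms.

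With μ = ln(median), M = exp(μ + σ²/2) and z = (ln 3 − μ)/σ, the share of short stays is P = Φ(z). Their contribution to the mean is S = M·Φ(z − σ), and that of longer stays is L = M − S. If a fraction a of short stays and b of the others are omitted, the mean among those kept is

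[(1 − a)S + (1 − b)L] / [(1 − a)P + (1 − b)(1 − P)].

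- Control: P = 0.2328, S = 0.488, L = 5.900, M = 6.388.
- Device: P = 0.3405, S = 0.681, L = 4.429, M = 5.110.
- True mean difference: 6.388 − 5.110 = 1.278 days. True log effect: ln(5/4) = 0.223.

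Example with a = 0.30 and b = 0.05:

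- Control: (0.70 × 0.488 + 0.95 × 5.900)/(0.70 × 0.2328 + 0.95 × 0.7672) = 5.947/0.892 = 6.668.
- Device: (0.70 × 0.681 + 0.95 × 4.429)/(0.70 × 0.3405 + 0.95 × 0.6595) = 4.685/0.865 = 5.417.
- Difference: 1.251 days, which is −2.0%.

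The log effect uses the same weights with μP − σφ(z) as the contribution of short stays.

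| Omitted: short / other stays | Mean difference, days (change) | Log effect (change) | Omitted of 150 |
|---|---|---|---|
| 10% / 5% | 1.274 (−0.3%) | 0.221 (−1.1%) | 10 |
| 20% / 5% | 1.265 (−1.0%) | 0.215 (−3.5%) | 14 |
| 30% / 5% | 1.251 (−2.0%) | 0.209 (−6.4%) | 18 |
| 50% / 5% | 1.211 (−5.2%) | 0.192 (−13.9%) | 27 |
| 5% / 10% | 1.281 (+0.2%) | 0.225 (+1.0%) | 13 |
| 5% / 20% | 1.285 (+0.6%) | 0.230 (+3.0%) | 24 |
| 5% / 30% | 1.285 (+0.6%) | 0.234 (+5.0%) | 34 |

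The range was then widened to medians of 4, 5 and 7 days and log-SDs of 0.5, 0.7 and 0.9, with omission of up to 30%. If mainly short stays are omitted, the mean difference changes by −3.8% to +1.7% and the log effect by −7.1% to −0.5%. If mainly longer stays are omitted, the changes are −4.1% to +3.6% and +0.4% to +7.5%.

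**4. No true effect.** If both arms follow the same omission rule, there is no bias. If the arms differ, there can be. Assume median 5 days and log-SD 0.6 in both arms, 10% of stays of 4 days or more omitted, and stays under 4 days omitted at 40% in one arm and 10% in the other. Overall omission is then 20.6% v 10%, and the arm that loses more short stays appears about 0.43 days longer.

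**5. Precision.** Omission unrelated to stay causes no bias but loses data. Losing 5% to 15% widens the length-of-stay interval by 1/√0.95 = 1.026 to 1/√0.85 = 1.085, that is by 2.6% to 8.5%. If all 46 budgeted losses occurred, the difference detectable with 80% power, (1.960 + 0.842)·√(2/n), would be 0.55 SD with 52 per arm, against 0.46 SD with 75.

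**The case against.** The strongest reply has four parts.

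- **Section 13 softens the rule.** It makes withdrawal discretionary and keeps the data, so exclusion might not happen. The two sections do disagree. But keeping data is not a promise to analyse them, and discretion leaves a choice about who is analysed to be made after randomization.
- **Coordinated discharge makes the event rare.** It may well do so, and the figures above are small in that case. The plan still has a rule for when coordination fails, and that rule is the problem.
- **Length of stay is not the powered outcome.** True: section 6 powers FVC/FEV1, and section 11 (Data Analysis Plan) applies the t-test only to IS and FVC/FEV1, with correlations for stay and ambulation. Stay is nonetheless in the hypothesis, and section 3 says that it will be compared between groups.
- **The margin from 104 to 150 absorbs incomplete data.** It protects power for FVC/FEV1: a 15% loss leaves about 127. It does not protect against selective omission or restore precision for stay.

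It stands that the case rests on analysing patients as randomized and not on a demonstrated large bias. The documents give no evidence that omission would differ by arm.

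**Conclusion.** The concern holds. Followed as written, section 10 removes randomized patients from outcomes for which their data exist, and nothing elsewhere in the document puts them back. If coordination works and both arms lose patients by the same rule, the effect on length of stay is small and of open direction: within about 4% on the mean difference and 8% on the log effect over the range of assumptions tried. It becomes material if coordination often fails or if omission differs by arm. All of these bias figures rest on assumed stay distributions and omission rates. No effect on FVC/FEV1 or on time to ambulation is estimated, because the documents give no basis for one. The rule should be fixed because it is avoidable and cheap to correct.

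**What to change.** Replace the omission sentence in section 10 with an analysis-set statement:

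- All randomized patients are analysed in their assigned arm.
- Length of stay and time to ambulation are taken from the chart for everyone who has not withdrawn permission.
- All available IS and FVC/FEV1 values are used. Section 11 should name the time point that the t-test addresses and say how a missing final value is handled there.
- Missed final tests are reported by arm, with reasons.

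Reword section 13 to agree, so that missing the final test does not remove a patient from the analysis. An analysis limited to patients with the final test may be kept as a sensitivity analysis.

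The cost is a written amendment with the approval of the responsible party and the local IRB, as the regulatory obligations under section 33 require, plus slightly more chart abstraction and analysis. No visits or patients are added, and the required sample size does not change.
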